We specified hypotheses based upon the pattern of results found through child age 12, and separated them into primary and secondary hypotheses. Following the original formulation of hypotheses, we edited them to take into account results from the earlier Elmira trial¹⁰ that were analyzed following the submission of the proposal for the current phase of follow-up in Memphis. We had originally hypothesized that program effects would be more pronounced for mothers and children living in the most disadvantaged neighborhoods in Memphis, but realized as these data were being gathered that virtually all of the participants in the Memphis trial lived in neighborhoods that were so disadvantaged that there was little meaningful variation among neighborhoods, and therefore removed this aspect of our hypotheses. We also found that it was impossible to consistently gather information from children's school records on outcomes like conduct grades from hundreds of schools, so substituted high school graduation as a secondary outcome. These refined hypotheses were specified prior to the completion of data gathering and any analysis of treatment-control differences. We specify the original hypotheses and then indicate the revised hypotheses for maternal and child outcomes. Compared to control-group counterparts:

Original Maternal Outcomes Hypotheses

1. **(Primary)** The program will continue to improve maternal life-course (fewer short inter-birth intervals, less use of welfare, more stable partner relations), especially for mothers with higher psychological resources.
2. **(Secondary)** The program will reduce maternal substance use disorders (SUDs) and depression, effects that will be more pronounced for a) mothers with low psychological resources, and b) those living in the most disadvantaged neighborhoods at registration.

Revised Maternal Outcome Hypotheses

1. **(Primary)** The program will continue to improve maternal life-course (reflected in total costs of welfare – SNAP, TANF, Medicaid), especially for mothers with higher psychological resources.
2. **(Secondary)** The program will reduce maternal substance use disorders (SUDs) and depression.

Original Child Outcomes Hypotheses

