3. **(Primary)** The program will improve the health and development of firstborn children who will exhibit: a) superior cognitive, language, and academic functioning, and executive cognitive functioning (ECF); b) less depression and anxiety; c) fewer failed conduct grades and school disciplinary actions, d) less violent behavior and gang membership, and fewer arrests, juvenile detentions, and convictions – especially for crimes involving interpersonal violence.

4. **(Primary)** The program will reduce youth risk for HIV infection, including a) use of substances and SUDs; b) risky sexual behaviors; c) sexually transmitted infections (STIs) and d) pregnancies.
5. **(Primary)** Program effects on youth will be more pronounced for a) males, b) those born to low-resource mothers, and c) those living in the most disadvantaged neighborhoods at registration.

Revised Child Outcome Hypotheses

3. **(Primary)** The program will improve the health and development of firstborn children who will exhibit: a) superior cognitive, language, and academic functioning; b) less depression and anxiety; d) less gang membership, and fewer arrests, convictions, and self-reported antisocial behavior - especially for crimes involving interpersonal violence.
4. **(Primary)** The program will reduce youth risk for HIV infection, pregnancies, births, use of substances, and SUDs.
5. **(Secondary)** The program will improve firstborn children's executive cognitive functioning (ECF); and rates of high school graduation.
6. **(Primary)** Program effects on cognitive, language, and academic functioning, and executive cognitive functioning will be more pronounced among those born to low-resource mothers and on arrests and convictions among females.

Maternal and Child Outcomes (Not Revised)

7. **(Secondary)** Program effects on mothers and youth, in preliminary analyses, will be more pronounced for those with genetic vulnerabilities:
 - a. Effects on youth depression and anxiety will be greater for those with low-activity genotypes (S/S, L_G/L_G, S/L_G) of the serotonin transporter gene (*SLC6A4*) promoter polymorphism, 5-HTTLPR, compared to those with high-activity genotypes (L_A/L_A); effects on these outcomes will be of intermediate magnitude for those with intermediate activity-level genotypes (S/L_A, L_A/L_G).

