Relationship with Current Partner. We interviewed mothers regarding their current partners, lengths of their relationships, whether they were married or cohabiting, whether he is the father of index or subsequent children, his employment, education, criminal involvement, and quality of relationships with their children. We also assessed the degree to which mothers are committed to their partners, have effective communication, and experience conflict.¹⁹¹ The primary outcome is the duration of their relationship counted in months.

Domestic Violence. We administered Straus's Conflict Tactics Scales used in earlier phases of this trial to obtain information on the degree to which mothers experienced violence from any of their partners during the 6-month period preceding the interview.¹⁹² These data have not yet been compiled into analysis variables.

Maternal Depression and Anxiety. We administered the Beck Depression Inventory (BDI-II) to measure depression severity.¹⁹³ Women also completed the Beck Anxiety Inventory (BAI), a 21-item self-report check-list developed to distinguish anxiety symptoms from depression.¹⁹⁴ Our primary outcomes were whether or not they crossed the borderline or clinical cut points on these inventories.

Vulnerability Genes. We gathered saliva using Oragene technology to obtain DNA for genotyping. Our description of gathering and processing DNA and conducting genetic analyses is provided below.

Other Maternal Measures. While not the focus of specific hypotheses, we gathered information on a variety of maternal characteristics that will be useful in interpreting the results of our primary analyses and that are needed for an economic analysis, which we will conduct with support from a separate application. They include measures of maternal employment by interview; the degree to which

the father of the child (if not the current partner) is involved in the life of the firstborn child; and mothers' involvement with the criminal justice system.

Child Assessments

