Pregnancies. We assessed the number and outcomes of pregnancies (miscarriage, therapeutic abortion, still birth, live birth) for both males and females, focusing on the timing and number of pregnancies. The primary outcomes are the count of pregnancies and timing of first pregnancy.

High School Graduation and GEDs. We obtained permission to review children's school records to assess high school graduation. We had hoped to assess conduct grades, disciplinary actions, and school attendance records but found that such records were incomplete and extraordinarily difficult to obtain from the many different school systems that the children attended. We therefore settled for official records of high school graduation and GEDs. We conducted these reviews after all youth would

have graduated from high school had they been on track for graduation (the youngest child being age 20 at review). We employed self-reports of high school graduation and GED completion and validated self-reports with official records in all but 10 cases. Our primary outcome was whether the child had graduated from high school.

Violent Criminality and Gang Membership. Following the National Youth Survey,²²⁵ we interviewed youth to assess whether they had engaged in any of the following categories of criminal behavior over the life-course: felony assault, felony theft, robbery. We aggregated their responses into a scale of interpersonal violent offending over the life-course that included self-report of these types of behaviors plus having been convicted of a violent offense. We additionally derived a variable for whether or not the child reported being a member of gang prior to age 18.

Arrests, Convictions, and Juvenile Detention. We assess by maternal, other custody and youth interview the number of times the youth were arrested, convicted, and sent to juvenile detention, and the offenses that led to the arrests. Using a life history calendar, the dates of arrests and the reasons. The primary outcomes consisted of the count of arrests and convictions as well as counts of arrests and convictions for violent offenses.

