Inclusion of Gene Activity Classification Factors. Some of our models included classification factors for functional classifications (activity variants) of the polymorphisms hypothesized to moderate program impact in this trial (5-HTTLPR, MAOA-LPR, and COMT Val158Met); we were not interested in genotypes per se, but rather functional classes that group genotypes by activity level (low – L, high - H or intermediate - I). In the case of 5-HTTLPR, L_G and S alleles are both low-activity variants that lead to low expression; from the analysis standpoint, the low-activity genotypes (L_G/L_G, S/S, and L_G/S) were grouped into the low-activity class; the high activity genotypes (L_A/L_A) into a high-activity class; and the remaining genotypes (L_A/L_G and L_A/S) grouped into an intermediate class. We used a similar approach with MAOA-LPR and COMT Val158Met. In the case of the X-linked MAOA-LPR, we grouped males into high and low expression allele groups and excluded females from analyses. In the COMT Val158Met analyses, we excluded non-African ancestry participants.

Tests of Hypotheses

Maternal Outcome Hypotheses

Hypothesis 1 (primary): The program will continue to improve maternal life-course reflected in total costs for welfare (SNAP, AFDC/TANF, and Medicaid), especially for mothers with high psychological resources. We tested Hypothesis 1 by examining the primary maternal life-course outcome (public expenditures for SNAP, AFDC/TANF and Medicaid) in our primary model, estimating public expenditures for these benefits over time, which included a factor for T and P, the interaction between these classification factors (T x P), and a set of covariates. For the public benefit expenditure outcome, we analyzed the data in mixed models that included, in addition to the core model terms, women as levels of a random factor, a fixed repeated measures classification factor for time (first-born child age) of assessment, and all interactions of time with the other fixed classification factors. We examined the treatment–control difference summing across levels of maternal psychological resources, and conducted planned contrasts for women in the high-resource group.

Hypothesis 2 (secondary). The program will reduce maternal SUDs and depression. We examined SUDs and depression by examining planned contrasts within the classification structure specified for Hypothesis 1, using generalized linear models, logistic for depression and SUD.

Child Outcome Hypotheses

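### Primary hypotheses H3, H4 and H6 each bundle several separately tested outcomes with no stated rule for support, and the measures section calls other outcomes primary that the revised hypotheses make secondary or omit

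*Protocol*

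**What the plan says.** Under Hypotheses for Primary Grant, the protocol says that the investigators specified hypotheses and "separated them into primary and secondary hypotheses". It then gives original and revised versions. In the revised set, H1, H3, H4 and H6 are primary; H2, H5, H7 and H8 are secondary.

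- **H1** concerns maternal life-course "reflected in total costs of welfare – SNAP, TANF, Medicaid". Tests of Hypotheses examines the overall difference and says that the investigators "conducted planned contrasts for women in the high-resource group".
- **H3** covers cognition, language, achievement, depression and anxiety, gang membership, arrests, convictions and self-reported antisocial behavior. Each child outcome is examined in its own model.
- **H4** states: "The program will reduce youth risk for HIV infection, pregnancies, births, use of substances, and SUDs". Its methods are described as nearly identical to those for H3.
- **H5**, secondary, covers "executive cognitive functioning (ECF); and rates of high school graduation".
- **H6**, primary, states: "Program effects on cognitive, language, and academic functioning, and executive cognitive functioning will be more pronounced among those born to low-resource mothers". It adds a greater effect on arrests and convictions among females. It is tested by treatment contrasts within the subgroup.

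The measures section uses its own *primary outcome* labels. Under Arrests, Convictions, and Juvenile Detention: "The primary outcomes consisted of the count of arrests and convictions as well as counts of arrests and convictions for violent offenses". Under Relationship with Current Partner: "The primary outcome is the duration of their relationship counted in months". The same label is given to high school graduation, the facial recognition score, maternal substance abuse or dependence, and the maternal depression and anxiety cut points.

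Tests of Hypotheses goes through the hypotheses one by one with models and contrasts. The only explicit decision criterion is for mediation under secondary H8.

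**The concern.** Three of the four primary hypotheses are composite statements, but their components are tested singly. The protocol does not say what pattern of results would support the composite. If births fell but HIV risk, substance use and substance use disorders did not change, a reader could not tell from the protocol whether H4 was supported. With many components, some nominally significant result under a primary heading is to be expected by chance, and it would carry the weight of a pre-specified primary finding.

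The second problem is that two parts of the protocol give different answers to the question of what is primary. Someone writing up high school graduation could cite the measures section for primary status and ignore its place in secondary H5. Relationship duration could be reported as primary although partner stability was dropped from revised H1.

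**Working it through.** The protocol states no significance level, number of tests or familywise error rate, so there is no figure of its own to reproduce. The count is built from the revised hypotheses and the outcomes named in the measures section.

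**Count of primary tests**

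| Hypothesis | Components | Tests |
|---|---|---|
| H1 | total welfare cost: whole sample, high-resource mothers | 2 |
| H3 | Matrices, PPVT, PIAT math; internalizing; gang membership; arrests, convictions, violent arrests, violent convictions; violent-offending scale | 10 |
| H4 | HIV risk score; pregnancy count; time to first pregnancy; births; substance use; substance use disorder | 6 |
| H6 | 3 cognitive, language and math contrasts and 4 executive-function contrasts in the low-resource group; arrests and convictions in females | 9 |
| Total | | 27 |

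The four executive functions are those listed in Table 4. A narrow reading gives 2 + 8 + 5 + 6 = 21. A broad reading gives 6 + 12 + 7 + 12 = 37; its six for H1 would be three benefit programs by two contrasts. H6 is counted with two of the four arrest and conviction counts; using all four gives 29, inside that range.

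**Independent tests.** Assume 0.05 two-sided per test and no true effect anywhere. P(at least one false positive) = 1 − 0.95^k.

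- H1: 1 − 0.95^2 = 9.8%
- H3: 1 − 0.95^10 = 40.1%
- H4: 1 − 0.95^6 = 26.5%
- H6: 1 − 0.95^9 = 37.0%
- All 27: 1 − 0.95^27 = 75.0% (21 tests: 65.9%; 37 tests: 85.0%)
- Expected false positives: 27 × 0.05 = 1.35

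**Results favouring the program only.** At 0.025 per test in that direction, 1 − 0.975^27 = 49.5%.

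**Allowing for dependence.** The 27 contrasts were simulated under the global null with 200,000 draws. Subgroup contrasts were nested in the whole sample, the four resource-by-sex cells were of equal size, child outcomes shared a common correlation, and welfare cost was uncorrelated with child outcomes.

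| Correlation among child outcomes | Either direction | Favouring the program |
|---|---|---|
| 0 | 72.6% | 47.0% |
| 0.3 | 64.7% | 35.7% |
| 0.5 | 54.7% | 29.1% |
| 0.7 | 43.5% | 22.6% |

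**Labels side by side**

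| Outcome | Revised hypotheses | Measures section |
|---|---|---|
| High school graduation | secondary (H5); also introduced as a secondary substitute under Hypotheses for Primary Grant | primary |
| Facial recognition (an executive function in Table 4) | main effect secondary (H5) | primary |
| Maternal substance use disorder, depression | secondary (H2) | primary |
| Relationship duration | not in revised H1 | primary |

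Subsequent-pregnancy outcomes are also called primary, but the same paragraph says that they were dropped, so that entry resolves itself.

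**The case against.** The strongest objection is that a significance level, multiplicity procedure and success criterion commonly sit in a statistical analysis plan, which may exist here and is not shown. That stands in part: the absence of an adjustment method would not be a finding by itself. A reader might also infer that the protocol lets one significant item carry a whole hypothesis. It nowhere says so. But the protocol fixes the composition of the primary set and sets out its tests hypothesis by hypothesis. A separate plan could add a rule, but it would not make these sections agree.

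Three stronger readings are tempting and are not supported.

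- **All four primary hypotheses are lists.** H1 is not. It is one aggregate outcome with an overall test and one planned contrast.
- **A chance finding in favour of the program is more likely than not.** The hypotheses are directional. On the 27-test count the favourable-direction probability is about 23% to 50%. The 75% figure counts either direction and assumes independence.
- **Executive functioning is ranked contradictorily and must be demoted in H6.** H5 concerns the whole-sample effect and H6 the effect in children of low-resource mothers. These are different estimands and may hold different ranks. The protocol gives a rationale: earlier child effects were larger in that group, and the achievement effect from age 6 to 12 was confined to it. The original H5 already made low-resource moderation primary. Ranking a subgroup effect above its main effect is unusual and goes unexplained for executive functioning specifically, but demotion would be a preference.

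On the labels, *primary outcome* in the measures section may mean the main variable for a construct. That is plausible, and Tests of Hypotheses does show each hypothesis's rank. But the protocol never explains the second usage, and outcomes that really are primary, such as the arrest and conviction counts, carry the same words.

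**Conclusion.** The concern holds in a limited form. H3, H4 and H6 are primary, have several separately tested components each, and come with no stated rule for when they are supported. Some outcomes are labelled primary in one section and secondary, or absent, in another.

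The size rests on a count of 27 (defensibly 21 to 37), an assumed two-sided 0.05 level and a global null. The chance of at least one false positive under a primary label is 75% if independent (66% to 85% over the range of counts), and 44% to 65% with nesting and correlations of 0.7 to 0.3. For results favouring the program it is about 23% to 50% on the 27-test count. Every one of these is several times 5%. The label conflicts depend on none of these assumptions.

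**What to change.** 1. List the primary outcomes once, following the revised hypotheses.
2. In the measures section, replace *primary outcome* with *main measure* for every outcome under a secondary or dropped hypothesis: high school graduation, facial recognition, maternal substance use disorder, maternal depression and anxiety, relationship duration and subsequent pregnancy.
3. State whether the executive-function contrast in the low-resource group is meant to be primary although the main effect is secondary. Do not re-rank it once results are seen: the protocol says that the revised hypotheses were set before data gathering was complete and before any treatment-control comparison.
4. Within each of H3, H4 and H6, report Holm-adjusted p-values beside the raw ones, and describe outcomes that do not survive as nominal. The smallest p-value would need to reach 0.05/10 = 0.005 in H3, 0.05/6 = 0.0083 in H4 and 0.05/9 = 0.0056 in H6 as now written.

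The work is relabelling and arithmetic on existing p-values, with no new data. The cost is that some nominal findings lose confirmatory status. Error is also controlled only within each hypothesis. With H1's two contrasts unadjusted and independence assumed, the overall chance of a false positive is 1 − 0.95^2 × 0.95^3 = 22.6%, and the report should say so. Control across all 27 tests by Bonferroni would need 0.05/27 = 0.00185 per test.

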by running *Structure* 2.2 (<http://pritch.bsd.uchicago.edu/software.html>). AIMS genotype data for each subject were analyzed individually along with the data for the 51 CEPH populations to identify population substructure and compute individual ethnic factor scores. The mean (SE) African ancestry score was 0.76 (0.01) (median, 0.83) for mothers and youth. A subset of 34 youth had > 0.54 European ancestry (EA) (median = 0.93). When these were removed from the dataset, the African ancestry score of the resulting AA youth was mean (SE), 0.82 (0.00) (median = 0.83).

Promoter Region of the Serotonin Transporter (5-HTTLPR). The promoter region of the serotonin transporter gene (*SLC6A4*) was used to characterize genetic vulnerability to depression and to test whether 5-HTT gene variation moderates the influence of child maltreatment and life stress on depression. The promoter activity of the 5-HTT gene, located on 17q11.2, is modified by sequence elements within the proximal 5' regulatory region, designated the 5-HTT gene-linked polymorphic region (5-HTTLPR). The short ("S") allele in 5-HTTLPR is associated with lower transcriptional efficiency of the promoter compared with the long ("L") allele. An additional functional allele has been discovered in the HTTLPR locus: an A to G substitution in the first of the 2 extra repeats defining the L allele.¹⁴⁴ This polymorphism accounts for more of the inter-individual variation in 5-HTT expression.¹⁴⁴ The 3 alleles are S, L_A and L_G; their frequencies are given in Table 5. The L_G and S alleles are functionally equivalent: both cause reduction of expression. On a functional basis, S and L_G can be grouped for genetic analyses, yielding 3 genotypes, low/low, low/high and high/high. Frequencies of these genotypes are approximately 1:2:1 in African-Americans and Caucasians. Those individuals with either S/S, S/L_G, or L_G/L_G genotypes were grouped for analysis to reflect the vulnerable segment of the sample. Details of the methods used for genotyping are given in Hu et al.¹⁴⁴

Table 5. Distribution of HTTLPR Genotype and Allele Frequencies in Several Populations

Population	N	Frequency of Genotype						Freq. of Allele		
		SS	SL _A	SL _G	L _A L _A	L _A L _G	L _G L _G	S	L _A	L _G
U.S. whites group 1	297	.16	.33	.09	.26	.14	.03	.37	.49	.14
U.S. whites group 2	286	.12	.37	.08	.22	.18	.02	.35	.50	.15
African-American	624	.07	.25	.12	.27	.23	.06	.25	.51	.24

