The primary analyses made use of general linear model methods and their extensions. The focus was on full model specification to account for all sources of variation, and a full examination of interactions among model factors. The primary classification factors for examination in our models, as determined by our hypotheses and earlier work, include treatments (Control vs. Nurse Visited - T), maternal psychological resources (low versus high – P), and sex of child (S). Standard covariates included an index of household poverty, maternal beliefs associated with child abuse, and for child outcomes, age of the child at the 18-year interview. Genetic analyses included the gene as an additional classification factor and were interacted with treatment status only (see more information below). We employed pared-down versions of full model specification when we had infrequently occurring outcomes (e.g. convictions for interpersonal violence). In general the approach involved beginning with a fully specified model and continuing to eliminate non-significant interactions unless a specific a priori hypothesis forced the interaction term(s) into the model.

Continuous variables were run with a general linear model; dichotomous variables with binomial error distributions; low frequency count variables with negative binomial distributions. For outcomes measured over the life course, the above models were extended to mixed or generalized mixed models to account for correlated data (random effects for time with unstructured variance terms). Subsequent children analyses were also run with mixed or generalized mixed models to account for correlation within the same family. We were interested in the treatment effects for subsequent children alone, as opposed to an overall family effect that would include the first born children.

We employed Cox proportional hazard models²³² for outcomes with a survival component. We present in the tables adjusted hazard rates at age 18 since the vast majority of the sample was interviewed after their 18th birthday but rapidly drops off after this date. The methods used for the mortality analyses can be found elsewhere.¹¹

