Hypothesis 7 (secondary): Program effects on mothers and children will be more pronounced for those with genetic vulnerabilities: a) Effects on youth depression and anxiety will be greater for those with the low-activity 5-HTTLPR genotypes (S/S, L_G/L_G, S/L_G) compared to those with the high-activity genotypes (L_A/L_A); effects on these outcomes will be of intermediate magnitude for those with intermediate activity genotypes (S/L_A). We will test this hypothesis by adding a 3-level 5-HTT genetic vulnerability factor to the statistical model and examining treatment–control differences within levels of genetic risk. b) Effects on youth violent antisocial behavior, SUDS, and risky sexual behavior, including STIs and pregnancies, will be more pronounced among males with the MAOA-LPR low-activity alleles and among both males and females with the Val/Val (H/H) COMT genotype. We will repeat the analysis of child outcomes, substituting first a factor that classifies the sample into groups of MAOA alleles that confer high versus low activity, focusing the treatment contrast on males within the low-MAOA category; we will repeat this analysis for both males and females, substituting the COMT genotype as the genetic vulnerability factor, focusing the treatment contrast on the high-activity subgroup (Val/Val). c) Effects on maternal SUDs will be concentrated among those mothers with the Val/Val COMT genotype. In testing this hypothesis, we again will add the COMT genotype (H/H, H/L, LL) to our standard model and repeat the analysis of maternal SUDs, focusing on our planned treatment contrast on the H/H subgroup. d) Effects on child outcomes will be more pronounced among children born to mothers with either: 1) the low-activity 5-HTTLPR genotypes; or 2) 2 copies of the high-activity COMT Val158 alleles (COMT-H). In testing this hypothesis, we again will add the 5-HTTLPR genetic risk factor to our standard models and repeat the analysis of child outcomes, with planned contrasts focusing on treatment–control differences within the low-activity 5-HTTLPR subgroup defined by mothers’ having either high- low- or intermediate activity classifications. Given limited statistical power to examine treatment contrasts within any one of these subgroups alone, we also will create a maternal genetic risk factor based upon whether mothers possess any one of these risk genotypes and then re-run the analysis of treatment-control differences focusing on planned comparisons within the high genetic risk factor defined by mothers possessing either one of these 2 risk genotypes.

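### Hypothesis 7a is a claim about differences in program effect between 5-HTTLPR classes, but its stated test looks only within each class

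*Protocol*

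**What the plan says.** The hypothesis stands in the protocol under Maternal and Child Outcomes (Not Revised), item 7a. It has two parts. The first is pairwise: "Effects on youth depression and anxiety will be greater for those with low-activity genotypes" than for those with the high-activity genotype. The second concerns the middle class: "effects on these outcomes will be of intermediate magnitude for those with intermediate activity-level genotypes". Together they predict low > intermediate > high.

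The test is stated in Tests of Hypotheses, Hypothesis 7, part a: "We will test this hypothesis by adding a 3-level 5-HTT genetic vulnerability factor to the statistical model", followed by "examining treatment–control differences within levels of genetic risk".

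Two sentences in Statistical Models and Methods of Analysis bear on this. One says "Genetic analyses included the gene as an additional classification factor and were interacted with treatment status only". The other describes model reduction as "continuing to eliminate non-significant interactions unless a specific a priori hypothesis forced the interaction term(s) into the model".

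The section on the serotonin transporter promoter treats S and L_G as functionally equivalent, "yielding 3 genotypes, low/low, low/high and high/high". The classes therefore correspond to 2, 1 and 0 low-activity alleles.

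The intermediate class is not defined consistently. The hypothesis list and the section Inclusion of Gene Activity Classification Factors both include S/L_A and L_A/L_G. Part a of Hypothesis 7 in Tests of Hypotheses lists only S/L_A.

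**The concern.** A statement that the effect is greater in one class than in another is a statement about a difference of differences. The procedure given for 7a produces three separate treatment-control differences and does not compare them. Followed as written, it invites the familiar misreading in which a significant result in one subgroup and a non-significant result in another is taken as evidence that the two differ. That pattern arises easily when the effect is uniform and each class is small.

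A uniform effect is a realistic case here, because revised Hypothesis 3 (primary) predicts less depression and anxiety in the program group as a whole. At stake is whether a claim of genetic moderation could be reported without ever having been tested.

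**Working it through.** The protocol gives no sample size, power or alpha for 7a, so there is no figure of its own to reproduce. Its stated genotype ratio of about 1:2:1 can be checked against Table 5 and agrees.

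**Inputs from the protocol**
- Class shares (Table 5, African-American row): low .07 + .12 + .06 = .25; intermediate .25 + .23 = .48; high .27.
- Youth assessed at 18 years (Table 2): 435 control, 194 nurse-visited, 629 in all.

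**Assumptions not in the protocol:** two-sided 0.05; a continuous outcome in SD units; Table 5 shares apply to this sample; 100% of the 629 genotyped, or 80% (348 and 155).

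**Standard error of the program effect in class k:** SE_k = sqrt(1/(435·f_k) + 1/(194·f_k)). This gives 0.173 (low), 0.125 (intermediate) and 0.166 (high). At 80% genotyped it gives 0.193, 0.139 and 0.186.

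**Chance that the low class is significant and the high class is not, under a uniform effect δ.** With P_k = 1 − Φ(1.96 − δ/SE_k), the chance is P_low × (1 − P_high):

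| δ (SD) | genotyped | P_low | P_high | low significant, high not |
|---|---|---|---|---|
| 0 | 100% | .025 | .025 | 2.4% |
| 0.2 | 100% | .211 | .225 | 16.4% |
| 0.3 | 100% | .412 | .439 | 23.1% |
| 0.2 | 80% | .178 | .188 | 14.4% |
| 0.3 | 80% | .342 | .365 | 21.7% |

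Simulation at full genotyping shows the three estimates also falling in the predicted order in 9.5% of trials (δ = 0.2) and 14.1% (δ = 0.3).

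**Between-class contrasts at full genotyping**
- Low minus high: SE = sqrt(0.173² + 0.166²) = 0.240.
- Slope on allele count, inverse-variance weighted: SE = 0.120 per allele, or 0.240 over two alleles. The slope weights the class effects by +0.49, +0.02 and −0.51, so it is in effect half the low-minus-high difference. The middle class, about half the sample, contributes almost nothing.

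| True effects (low / intermediate / high, SD) | low vs high | slope | unordered 2-df test |
|---|---|---|---|
| 0.4 / 0.2 / 0 | 39% | 39% | 30% |
| 0.6 / 0.3 / 0 | 71% | 71% | 60% |
| 0.6 / 0 / 0 | 71% | 69% | 77% |
| 0.6 / 0.6 / 0 | 71% | 72% | 79% |

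At 80% genotyped, power for the two graded patterns is 32% and 61% for either 1-df contrast, against 25% and 50% for the 2-df test.

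The last two rows show the limit of both 1-df contrasts. They are about as likely to be significant when the middle class equals one end as when it lies halfway.

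**The case against.** The strongest reply is that the interaction is already there. The gene is interacted with treatment, and 7a is just the kind of a priori hypothesis that keeps a term in the model. This stands as far as it goes: a reader might infer that the protocol has no means of comparing classes, and that would be wrong. But having the term in the model does not make it the criterion. The sentence that says how 7a will be tested names the within-class differences.

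A second reply is that the choice of contrast is ordinary analysis-plan detail. That would hold if the protocol were silent. It is not silent: it states a test, and that test does not answer the hypothesis.

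Third, the 14% to 23% is not the error rate of a stated rule, because no section says that a significant low class with a non-significant high class counts as support. This is correct. The figure shows how often the stated display would look like moderation when there is none.

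Fourth, a reader might infer that the three-level factor wastes power and that a trend test would recover it. The documents do not support this. The low-versus-high contrast comes directly from the three-level factor and has the same power as the slope. The gain is only over a 2-df omnibus test that no section names as the test of 7a, and under a threshold pattern the omnibus test does better. Nor would a significant slope establish the gradient, since it is nearly as likely under 0.6/0/0 or 0.6/0.6/0 as under 0.6/0.3/0.

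**Conclusion.** The concern holds in a limited form. Hypothesis 7a compares program effects between classes, and its stated test does not. With a uniform effect of 0.2 to 0.3 SD, a pattern resembling moderation appears in about 14% to 23% of trials. With no effect in any class it appears in about 2%.

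These figures rest on the assumptions listed above. The number genotyped is not given, and the SD-unit calculation does not carry over to the dichotomous borderline/clinical internalizing outcome that the protocol also creates (Behavior Problems and Mental Disorders). Power for 7a stays modest after the change: 32% to 39% for effects of 0.4/0.2/0 SD and 61% to 71% for 0.6/0.3/0.

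The conflict over the intermediate class is a separate inconsistency in the text. L_A/L_G makes up 23% of the Table 5 African-American sample, so the wording in Tests of Hypotheses leaves a large group without a class.

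Because 7a is secondary and described as preliminary, this is a minor point.

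**What to change.** Keep the three-level factor and the treatment-by-genotype term. In Tests of Hypotheses, part a of Hypothesis 7, add that:

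- the test of 7a is a single 1-df between-class contrast of treatment effects, either low versus high activity or the slope on number of low-activity alleles, chosen in advance;
- the three class-specific program effects are reported with confidence intervals as description;
- a significant contrast supports a larger effect in the low-activity than in the high-activity class. The word graded is used only if the intermediate estimate and its interval, or a departure-from-linearity check, are consistent with it.

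Make the intermediate class read the same in the hypothesis list, the gene classification section and Tests of Hypotheses.

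The cost is a few lines of wording and no new data. The drawback is some loss of power against the 2-df test if the true pattern is a threshold: at 0.6/0/0 SD, 69% for the slope (71% for low versus high) against 77%.
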